2. WHAT DOES THIS TRIAL ADD TO CURRENT KNOWLEDGE?

This is to our knowledge the first RCT looking at flexor tenotomies as a preventive treatment, and/or compared to conservative treatment. At the same time this is the first study looking at needle flexor tenotomies, as opposed to the classic tenotomies done by scalpel.

3. Hypothesis

We hypothesize that treating hammer, mallet and claw toe deformities in patients with type 1 and 2 diabetes, and impending ulcers (defined as nail changes, and hypercallosities at the predilection sites for ulcers associated with hammer, mallet and claw toe deformities) with needle tenotomy is a safe and effective treatment, and superior compared to offloading (conservative) treatment done by silicon spacer, insoles, felt, and/or therapeutic sandals

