4. AIM

The aim of the RCT is to evaluate the effect of needle tenotomy when treating impending ulcers associated with hammer, mallet and claw toe deformities.

The study is designed as a prospective RCT comparing needle tenotomy with conservative treatment, for patients with deformities and impending ulcers associated with the three deformities. Primary endpoint will be number of new ulcers incurred, defined as ulcers associated with hammer, mallet and claw toe deformities, placed on treated foot.

Secondary endpoints will be complications: infections (defined as ailment associated with procedure or ulcer, that is diagnosed as infection by attending health professional), transfer lesions (defined as impending ulcers or actual ulcers at anatomical sites associated with hammer, mallet and claw toes in patients with diabetes, on non-treated hammer, mallet and claw toes after surgical treatment), minor amputations (defined as amputations below ankle level), major amputations (defined as amputations at or above ankle level).

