5. STUDY I

5.1 Design

A prospective RCT involving patients with diabetes as well as one of the three deformities and an impending ulcer associated with the mentioned deformities. By randomization, patients will be allocated to either conservative treatment or tenotomy performed by needle.

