5.2 Patients

Inclusion criteria

- Patients aged 18 years or above
- Type 1 or 2 diabetes
- Hammer, mallet or claw toe deformity
- Impending ulcer associated with above mentioned deformities
- Able to understand written and oral information
- Ability to follow planned visits and treatment
- Able to provide informed consent in Danish and/or English

Exclusion criteria

- Revascularization procedure in the affected limb planned, or undertaken within the 4 weeks prior to screening
- Hammer, mallet and claw toe that are rigid in both MTP, IP joints
- Ulcer associated with hammer, mallet and claw toe deformities
- Toe pressure < 30mmHg
- Prior major amputations on affected or ipsilateral leg
- Other corrective operation is indicated to treat patients foot deformities as deemed by investigator
- Current treatment with cytotoxic drugs or with systemically administered glucocorticoids
- Treatment of foot ulcers with growth factors, stem cells or equivalent preparations within the 8 weeks prior to screening
- Likely inability to comply with the need for planned visits because of planned activity
- Participation in another interventional clinical foot ulcer-healing trial within the 4 weeks prior to screening
- Prior enrolment in this trial
- Judgement by the investigator that the patient does not have the capacity to understand the study procedures or provide written informed consent

Discontinuation of patients

- Patient discontinues assigned treatment for any reason, while not fulfilling one of the studies accepted endpoints
- Participants who withdraw from treatment will be asked to remain in the trial for follow-up, and data will continue to be collected and analyzed.
- Patient incurs a serious adverse event (SAE), defined as death or sepsis related to the study procedure

- Investigator decides to discontinue patient due to health or compliance reasons
- Patient misses 3 consecutive visits
- Patient misses 5 or more visits during the full treatment period

Patients who discontinue the study early will be invited to have a clinical visit before being discontinued.

Patients that are discontinued will revert to their normal treatment plan, and continue in their respective clinics.

Endpoints

- New ulcer incurred
 - When/if new ulcer is incurred pictures will be send to two external evaluators to be confirmed as new ulcer
- Patient reaches 12 month visit without incurring a new ulcer

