5.8 Statistics

All statistical analysis will be performed using the version of SAS currently used at our institute. All data will be analyzed on the intention to treat basis. All baseline data will be presented using appropriate summarizing statistics. Appropriate comparable statistical analysis will be applied to

- Incidence of new ulcer(s) in treated limb
- Mean time (in days) to healing of incision sites
- Incidence of minor amputations
- Incidence of major amputations

Odds-ratio will be applied to

- The incidence of secondary infection
- Pain in treated limb, associated with tenotomy
- Transfer lesion

Sample-size

The calculation is done with a Type 1 error rate (α) at 5%, and a power (1- β) at 80%. The primary endpoint is number of new ulcers incurred.

In the general diabetic population life time prevalence of diabetic ulcers has been reported at $15-25\%^{24}$, the yearly incidence in the same group is 6%. This study focuses on patients with a deformity reported to have a 1.5 hazard ratio²⁵, and signs of an impending ulcer like callus formation, which has been reported with a relative risk of 11^{26} . The incidence of new diabetic foot ulcers incurred by the study population is set at 10%, according to the above mentioned considerations.

The incidence in the intervention group (μ_A) is set at 6%, so the anticipated reduction in incidence is 4% compared to the incidence in the control group (μ_B) which as above mentioned is set at 10%. However, the numbers for incidence of new diabetic foot ulcers is an uncertain size, especially when looking at the specific group we are looking at, therefore the standard deviation (σ) is set at 10.

The calculator used is a 2 means, 2 sample, 2-sided equality calculator. The formula is

 $nB=(1+1/\kappa) ((\sigma z1-\alpha/2+z1-\beta)/(\mu A-\mu B))2$

nB= Sample size

 κ = The matching ratio

With the above described parameters, the sample size is 98 patients, which due to an expected dropout of 10% will be extended to 110 patients.

6. **Perspective**

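### The infection endpoint pools procedure infections with ulcer infections in one odds ratio, so harm and benefit can offset each other and the result cannot be read as a safety finding

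*Combined protocol and SAP*

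**What the plan says.** Section 4 (Aim) lists infection first among the complications that form the secondary endpoints: "infections (defined as ailment associated with procedure or ulcer, that is diagnosed as infection by attending health professional". Both sources count towards one endpoint. The definition is not limited to new ulcers or to the treated foot.

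Section 5.8 (Statistics) introduces a list with "Odds-ratio will be applied to", and the first item is "The incidence of secondary infection". The qualifier in that item is not defined and does not appear in section 4. No analysis by source of infection is planned.

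Section 3 (Hypothesis) states that "needle tenotomy is a safe and effective treatment". No safety margin or criterion is given. Under section 5.1 (Design), "patients will be allocated to either conservative treatment or tenotomy performed by needle", so by allocation one arm has a needle procedure and the other does not.

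The day 7 and 14, end and follow-up visits (sections 5.5.3 to 5.5.5) each record tenotomy complications, the incision site where applicable, and infection of any ulcer. Section 5.2 separately defines procedure-related sepsis as a serious adverse event.

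**The concern.** Tenotomy is expected to move the two parts of the endpoint in opposite directions. Among patients treated as allocated, procedure infections can only add to the tenotomy arm. Ulcer infections depend on how many ulcers occur, and section 5.8 plans on tenotomy reducing that number. A single odds ratio mixes the two, and its value depends on two rates that the plan does not state.

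Infection caused by the procedure bears directly on whether needle tenotomy is safe. Under the plan as written, no pre-specified result isolates it, and an odds ratio near 1 could be taken as reassurance even if the procedure does cause infections.

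A lesser point concerns ulcers already present at entry. The relevant exclusion in section 5.2 is "Ulcer associated with hammer, mallet and claw toe deformities", so a patient with an unrelated ulcer can be enrolled. Infection of that ulcer appears to count, although it reflects neither the procedure nor prevention of new ulcers.

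**Working it through.** The plan gives no rate, odds ratio or power for infection, so there is no figure of its own to reproduce. The check uses its planning values for ulcers and varies what is unknown.

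**Inputs from section 5.8.** New-ulcer incidence is 10% in control and 6% with tenotomy. Planned enrolment is 110 patients.

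**Assumptions.** Allocation is 1:1, giving 110/2 = 55 per arm; the ratio is not stated. Let f be the share of ulcers that become infected and are counted, and s the procedure infection rate. Neither is in the documents. The central case is f = 50%, s = 2%; the range is f = 30–60%, s = 0–5%. Procedure and ulcer infections are taken as independent.

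**Formulas.**
- Control risk: c = 0.10f
- Tenotomy risk: t = 1 − (1 − 0.06f)(1 − s)
- Odds ratio: [t/(1 − t)] / [c/(1 − c)]
- Chance that at least one arm of 55 has no infection: a + b − ab, with a = (1 − c)^55 and b = (1 − t)^55

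**Central case.** c = 0.10 × 0.50 = 5.0%. t = 1 − (0.97 × 0.98) = 4.94%. Odds ratio = (0.0494/0.9506)/(0.05/0.95) = 0.99. Taken separately, ulcer infections are 5.0% versus 3.0% (odds ratio 0.59) and procedure infections 0% versus 2%. For the empty-arm chance, a = 0.95^55 = 0.0595 and b = 0.9506^55 = 0.0616, which gives 0.1175, or about 12%.

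| f | s | Control | Tenotomy | Odds ratio | At least one arm with no infection |
|---|---|---|---|---|---|
| 30% | 0% | 3.0% | 1.8% | 0.59 | 49% |
| 30% | 5% | 3.0% | 6.7% | 2.33 | 21% |
| 50% | 2% | 5.0% | 4.9% | 0.99 | 12% |
| 60% | 0% | 6.0% | 3.6% | 0.59 | 16% |
| 60% | 5% | 6.0% | 8.4% | 1.44 | 4% |
| 10% (below range) | 2% | 1.0% | 2.6% | 2.63 | 68% |

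**Where the sources cancel.** Setting c = t gives s = 0.04f/(1 − 0.06f). That is 0.012/0.982 = 1.2% at f = 30%, 0.020/0.970 = 2.1% at f = 50%, and 0.024/0.964 = 2.5% at f = 60%. Away from these values the odds ratio leaves 1 in one direction or the other.

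**Precision.** With 3 infections in each arm of 55, the standard error of the log odds ratio is √(2/3 + 2/52) = 0.84, and the 95% interval is exp(±1.96 × 0.84), about 0.19 to 5.2. An odds ratio near 1 would not establish safety even without the mixing. When one arm has no infection the estimate is zero, infinite or undefined.

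**The case against.** Several stronger readings are tempting, and the documents do not support them.

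- **A reader might infer that harm and benefit will cancel.** That needs s to be close to 0.04f, and neither rate is given. The visit plan may also favour a small f. A new ulcer is a trial endpoint that leads to an end visit (sections 5.2, 5.5.3 and 5.5.4), so infections starting later may never be counted. With a small f, a pooled odds ratio would tend to show procedure harm: it is 2.6 at f = 10%, s = 2%.
- **A reader might infer that control patients can never have a procedure infection.** Section 7.3 lets control patients be offered tenotomy after an ulcer. Under intention to treat, a resulting infection would count in the control arm if follow-up continued. The statement holds for allocated treatment only.
- **A reader might infer that procedure infections go unrecorded.** The visit forms already register the sources largely separately. What is missing is a planned analysis; choosing one after seeing the data would be post hoc.
- **A reader might infer that the plan would call an odds ratio near 1 safe.** No section says so. One pooled odds ratio is itself the natural reading of section 5.8 rather than an explicit statement, because the term differs from section 4.

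Other points also stand. Any infection by randomised arm is a legitimate net measure. Sparse counts are not caused by pooling, and splitting makes them sparser. Pre-existing ulcers should balance on average by randomisation. None of this makes the pooled odds ratio informative about procedure harm, since its value cannot be interpreted without the components.

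**Conclusion.** The concern holds in a limited form, as a cheap improvement. The endpoint combines two sources of infection that tenotomy is expected to move in opposite directions, and no planned result separates them. The two can offset each other, so the pooled odds ratio cannot serve as a safety result.

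Under the assumed rates it is 0.99 in the central case and between about 0.59 and 2.3 over the range. The chance that at least one arm has no infection is about 12% (4–49%). These figures rest on the plan's 10% and 6% ulcer incidences, 1:1 allocation with 55 per arm, and assumed values of f and s. They illustrate the problem and do not predict the trial's result. The primary endpoint is not affected.

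**What to change.** Use one defined term for infection in sections 4 and 5.8, and pre-specify three results, built from items already registered at visits:

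1. **Procedure-site infection** among patients who had tenotomy: number, denominator and percentage with an exact 95% confidence interval. Show separately any tenotomy given to control patients after an ulcer.
2. **Infection of an ulcer new since randomisation on the index foot**, by randomised arm: risk difference with a score-type 95% interval in place of the odds ratio. State an observation window that is the same in both arms, and say whether infections after the end visit count.
3. **Any index-foot infection**, by randomised arm, as the net figure.

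Do not count infection of ulcers present at randomisation. State that safety will not be inferred from a pooled odds ratio near 1.

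The cost is one data field for the source of infection and a few lines in section 5.8, with no extra visits or patients. The downside is wide intervals for each component: with no procedure infection in 55 tenotomy patients, the one-sided 95% upper bound is still 1 − 0.05^(1/55) = 5.3%. The split makes that limit visible but does not supply the safety criterion that section 3 lacks.

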- Patient incurs minor or major amputation on either treated or nontreated limb
- Patient receives surgical intervention relevant for the study (other than planned in study)

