5.3.1 Needle Tenotomy Procedure

Patient is placed in seated posture with feet elevated. The toe(s) with hammer, mallet or claw toe deformity is anesthetized by a digital toe block with 1-5 ml of 1% lidocaine administered for each toe. The toe digital block is administered through a plantar approach, at the web level of the deformed toe(s), with a 0,6 mm diameter and 30mm long needle.

After anesthetizing the toe(s) the plantar aspect of the toe at web level is disinfected with an alcohol based disinfectant twice.

Both the long and short flexors are then severed with a 1.2mm diameter and 40mm long needle through a plantar approach, immediately proximal to the web level of the toe.

After the procedure a dry gauze bandage is applied and the patients treated foot/feet is/are elevated for 20 minutes to achieve haemostasis, and the bandage is checked for bleeding before discharge.

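### The transfer-lesion definition names no foot and has no counterpart in the conservative arm, so its planned odds ratio rests on an unclear count

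*Combined protocol and SAP*

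**What the plan says.** Section 4 introduces the secondary endpoints as complications ("will be complications: infections (defined as ailment associated with procedure or ulcer") and defines one of them as "transfer lesions (defined as impending ulcers or actual ulcers at anatomical sites associated with hammer, mallet and claw toes in patients with diabetes", lying "on non-treated hammer, mallet and claw toes after surgical treatment". No foot or side is named. Section 3 gives the meaning of an impending ulcer: "impending ulcers (defined as nail changes, and hypercallosities at the predilection sites for ulcers associated with hammer, mallet and claw toe deformities". Callus or a nail change alone is therefore enough.

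Other items do state a location. The primary endpoint in section 4 counts ulcers "placed on treated foot". Section 5.8 lists "Incidence of new ulcer(s) in treated limb" and also limits pain to the treated limb. The item after pain, transfer lesion, carries no limit. Section 5.8 assigns it an odds ratio.

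The visit descriptions in 5.5.3 to 5.5.5 ask staff to register complications that are associated with tenotomy, where relevant. They give no rule for deciding association and do not mention side.

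**The concern.** A transfer lesion is meant to capture harm from the procedure: load moves from a corrected toe to one that was left alone. A lesion on a foot that was not operated on may be no more than the patient's background disease. If such lesions are counted, the complication rate after tenotomy contains events that the operation may not have caused, and a true effect on the operated foot becomes harder to see. Section 3 claims that the procedure is safe, and this endpoint is part of the evidence for that claim.

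The between-arm comparison has a second problem. The definition applies only once surgery has taken place, yet an odds ratio needs events counted in both arms under one rule.

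**Working it through.** **Text check.** Take a patient operated on one foot who has a deformed toe on the other foot, and apply the section 4 definition to a new callus on that toe.

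| Element of the definition | Met? |
|---|---|
| Impending or actual ulcer | Yes; callus qualifies under section 3 |
| Site associated with the deformities | Yes, if at a predilection site |
| On a deformed toe that was not treated | Yes |
| After surgery | Yes |
| On the operated foot | Not required |

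No other section supplies the missing limit. For a conservative-arm patient the fourth element fails unless that patient is operated on later. Read literally, that arm has almost no way to contribute events, and the odds ratio has little or nothing in its denominator.

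**Size.** The plan states no transfer-lesion rate, so there is no figure to reproduce. All risks below are assumptions.

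*Effect on the complication rate.* Let b be the 12-month risk of a qualifying lesion per foot, equal in both feet, and r the within-patient correlation. The chance of a lesion on at least one foot is 2b − [b² + r·b(1 − b)]. With r = 0 this is 1 − (1 − b)².

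| b | r = 0 | ratio to b | r = 0.5 | ratio to b |
|---|---|---|---|---|
| 10% | 19% | 1.9 | 14.5% | 1.45 |
| 20% | 36% | 1.8 | 28% | 1.40 |
| 30% | 51% | 1.7 | 40.5% | 1.35 |

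Example for b = 20%, r = 0.5: 0.40 − (0.04 + 0.5 × 0.20 × 0.80) = 0.40 − 0.12 = 0.28.

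These ratios m apply only to patients with one-sided surgery and deformed toes on the other foot. If such patients are a fraction f of the arm and b is the same in the rest, the arm's rate is multiplied by 1 + f(m − 1). The documents do not give f.

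*Effect on the odds ratio, if both arms are counted by the same rule.* Let the same-foot risks be 20% (tenotomy) and 10% (conservative), and let the other-foot risk c be equal in both arms and independent of the study foot. The counted risks are A = 1 − 0.8(1 − c) and B = 1 − 0.9(1 − c). The odds ratio is [A/(1 − A)]/[B/(1 − B)]. The share of tenotomy-arm cases with a lesion only on the other foot is (A − 0.20)/A.

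| c | A | B | Odds ratio | Other foot only |
|---|---|---|---|---|
| 0 | 20% | 10% | 2.25 | 0% |
| 5% | 24% | 14.5% | 1.86 | 17% |
| 10% | 28% | 19% | 1.66 | 29% |
| 20% | 36% | 28% | 1.45 | 44% |
| 30% | 44% | 37% | 1.34 | 55% |

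Example for c = 20%: (0.36/0.64)/(0.28/0.72) = 0.5625/0.3889 = 1.45.

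**The case against.** The strongest reply is that the authors probably meant the operated foot. The word transfer implies a shift of load, and the visit forms ask only for complications associated with tenotomy. That is a causal filter, and it may well keep unrelated lesions on the other foot out of the data. This stands as evidence of intent. It does not settle the matter, because the explicit definition says something wider and no attribution rule tells staff at three sites how to decide.

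Section 5.3.1 also allows for one or both feet to be treated. Where both are operated on, the question of a non-operated foot does not arise. That limits the point to one-sided cases.

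Two stronger inferences should be resisted.

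- A reader might take "The toe(s) with hammer, mallet or claw toe deformity is anesthetized by a digital toe block" to mean that every deformed toe on the operated foot is cut, so that all counted lesions must come from the other foot. The sentence names no foot. If it means all deformed toes, it covers both feet and leaves none untreated. The inference needs all toes on one foot and none on the other, which the section does not say.
- A reader might point to the endpoint list in 5.2, where amputation counts on either limb, as a sign that both feet are meant here too. That line concerns amputation only. It shows that the authors can name both sides when they mean them, and leaves the silence on transfer lesions ambiguous.

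Finally, equal background risk in both arms, counted alike, weakens the contrast but does not bias it against tenotomy. That is correct. Bias against tenotomy would arise only if other-foot lesions were counted after surgery and not in the conservative arm, a possibility that the present wording leaves open.

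**Conclusion.** The point holds as a gap in a stated definition: side is unspecified, and the conservative arm has no counterpart for the planned odds ratio. A reader might go further and conclude that other-foot lesions will be counted as complications of tenotomy. The documents do not establish that; they leave it open.

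If such lesions are counted, the risk in affected patients rises by about 1.35-1.45 times with correlation 0.5, or 1.7-1.9 times with independence. Two feet of one patient share the same diabetes and neuropathy, so independence probably overstates the increase. Equal risk in both feet is also an assumption: the operated foot may have fewer untreated toes, or may carry a real transfer effect, so the ratio could lie outside these ranges. The fall in the odds ratio from 2.25 to 1.45 rests on assumed risks of 20%, 10% and 20%, independence, and the same counting rule in both arms.

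The primary endpoint and the sample size are untouched. This is a cheap improvement to one secondary endpoint.

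**What to change.** - In section 4, limit transfer lesions to the operated foot (or feet).
- Before randomisation, designate in every patient the study foot and the toes that would be operated on if allocated to tenotomy. Count lesions on the remaining deformed toes of that foot from day 0 in both arms, so that the odds ratio in 5.8 uses one rule.
- Record side for every lesion at each visit. Anatomical placement of impending ulcers is already recorded at inclusion and day 0, so the added work is small.
- Report lesions on the other foot separately, outside the complication count. Any unexpected pattern there would still be visible.

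The cost is a few words in sections 4 and 5.8, a side field, and a pre-randomisation entry. The downside is fewer counted events and a slightly wider interval for this secondary endpoint.

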5.5.1 Inclusion

Inclusion visit can only take place when written consent form is signed by patient, and filed in patient log.

The following procedures will be performed:

- In/exclusion criteria (see section 5.2)
- Baseline blood samples including:
 - o Hemoglobin A₁C
 - o Creatinine
 - o Estimated glomerular filtration rate
 - o Hemoglobin
 - o Albumin
 - o International normalized ratio
 - Low-density lipoproteins
 - o Leucocytes
 - o C-reactive protein
 - All blood samples are analyzed immediately, and nothing is preserved in biobank.
 The total amount of blood is evaluated to be less than 50ml pr. patient.
- Baseline physical examination including measurements of:
 - o Blood pressure
 - o Heart rate
 - Oxygen Saturation
 - o Heart and pulmonary auscultation
 - o Electro Cardiogram

- o Height
- o Weight
- Patient history including information on:
 - o Gender
 - male or female
 - o Diabetes type
 - 1 or 2
 - Duration of diabetes
 - measured in years with no decimal
 - o Duration of foot ulcer
 - measured in days
 - Competing diseases/comorbidity (ASA group is also registered)
 - By diagnosis and year of debut
 - o Current medicine
 - quantity and type
 - \circ Smoking
 - quantity and nature, present or past
 - Alcohol intake
 - quantity
 - Height, weight and BMI
 - In m(two decimals), kg(one decimal) and kg/m²(one decimal)
 - o Prior surgery on feet
 - Type and year
 - Prior ulcers of feet/legs
 - Location and year
 - Prior amputations
 - Location, type and year
 - o Prior/current history of Charcot's ailment
 - Debut year
 - Activity
 - Retinopathy
 - Simplex, proliferative and/or laser treated

- o Urinary albumin excretion rate
 - Normal, micro-, macro- or prior albuminuria
- Peripheral neuropathy
 - Yes/no
 - Pain associated with?
- Prior offloading therapy
 - Type
- o Relationship status
 - Married yes/no and/or living with partner yes/no
- Foot examination
 - Inspection of pressure point, and deformities
 - o Pulses
 - Deformities
- TSBP and ABPI
 - o TSBP and ABPI are performed by educated staff and results evaluated
 - Patients with TSB under 30 mmHg are referred to department of vascular surgery where deemed necessary
- Neurological assessment
 - o Biothesiometry tests are performed by educated staff
 - Monofilament testing is performed by educated staff
 - Neuropathy symptoms are examined and registered
- Randomization
 - o Randomization is performed in RedCAP
- Impending ulcer evaluation
 - Anatomical placement

5.5.2 Visit Day 0

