- Foot examination
 - Inspection of pressure point, and deformities
 - o Pulses
 - o Deformities
 - o New Ulcers

- Standard care & offloading
 - See section 5.3.2
- Tenotomy/conservative treatment application
 - The allocated treatment is performed
 - For details on tenotomy see section 5.3.1
 - For details on conservative treatment see section 5.3.2
- Impending ulcer evaluation
 - Anatomical placement
- Ulcer evaluation (if ulcer incurred)
 - Assessment of ulcer surroundings
 - Assessment of infection
 - Assessment of healing
- Measurement of longest length, width and depth in mm
- Measurement of area in mm³(length*width*depth)
 - Assessment of incision site (where applicable)
 - o Measurement of length, width and depth of ulcer(s) after debridement
- Categorizing by Texas Grading System
- Footwear assessment
 - Footwear and/or current offloading is evaluated
 - All patients in conservative and treatment group will be offered therapeutic sandals with customized insole at this visit
- Changes in medicine/new ailments
 - o Changes to the patient's medicine, and/or new diagnosis are registered

5.5.3 Visit Day 7, 14

The following is a specification of the above mentioned visits. If at any visit, before week 10, the impending ulcer has been deemed as progressed to active ulcer, patient is planned for end visit. If Patient incurs ulcer between visit day 14 and 3 month visit, patient contacts study personal to arrange end visit as soon as possible.

• Foot examination

- Inspection of pressure point, and deformities
- o Pulses
- o Deformities
- New Ulcers (not associated to registered impending ulcers)
- Changes in medicine/new ailments
 - o Changes to the patient's medicine, and/or new diagnosis are registered
- Standard care & offloading
 - See section 5.3.2
- Impending ulcer
 - Has impending ulcer progressed to active ulcer
- Ulcer evaluation (if relevant)
 - o Assessment of ulcer surroundings
 - o Assessment of infection
 - Assessment of healing
 - o Ulcer photo
 - o Measurement of longest length, width and depth in mm
 - Measurement of area in mm³(length*width*depth)
 - Assessment of incision site (where applicable)
 - o Measurement of length, width and depth of ulcer(s) after debridement
 - o Categorizing by Texas Grading System
- Footwear assessment
 - o Footwear and/or current offloading is evaluated
- Complications
 - Complications associated with tenotomy is registered (if relevant)
 - SAE is registered (if relevant)

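### Transfer lesion is defined so that controls on allocated treatment cannot have one, so its planned odds ratio will almost certainly be infinite or undefined

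*Combined protocol and SAP*

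**What the plan says.** Section 4 (Aim) lists transfer lesions among the secondary endpoints. They are impending or actual ulcers, at sites typical of these deformities, arising "on non-treated hammer, mallet and claw toes after surgical treatment".

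Section 5.8 (Statistics) states "Odds-ratio will be applied to" and lists three outcomes: secondary infection, tenotomy-related pain in the treated limb, and transfer lesion. It also says "All data will be analyzed on the intention to treat basis". It gives no control-arm version of transfer lesion, does not restrict the outcome to description in the tenotomy arm, and names no method for zero cells.

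Sections 5.1 and 5.3 give the control arm offloading without surgery. Section 7.3 lets controls be offered tenotomy if an ulcer occurs. In section 5.2 a new ulcer is an endpoint, and so is relevant surgery outside the plan.

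At Day 7 and 14 (section 5.5.3) the foot examination in both arms covers pressure points, deformities and "New Ulcers (not associated to registered impending ulcers". A separate item asks "Has impending ulcer progressed to active ulcer". The primary endpoint counts "ulcers associated with hammer, mallet and claw toe deformities, placed on treated foot".

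**The concern.** An odds ratio needs two groups, and the randomized arms are the only two that the plan names. The definition requires prior surgery, so a control on allocated treatment has no period in which the event can occur. The control cell is zero by definition, not by chance.

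Transfer lesion is the plan's named outcome for harm on neighbouring toes, in a trial whose hypothesis includes safety. The enrolled patients have deformities that section 1 calls predictors of ulcers, so uncut deformed toes carry some risk in either arm. As defined, the outcome counts that background risk in one arm only. A single tenotomy-arm lesion would give an infinite point estimate even if other deformed toes fared equally in both arms.

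**Working it through.** **Inputs.** The definition comes from section 4; the effect measure and analysis set come from section 5.8. The plan gives no expected transfer-lesion rate, so there is no figure of its own to reproduce for this outcome. For arm size I use its planned total: "the sample size is 98 patients, which due to an expected dropout of 10% will be extended to 110 patients". The sample-size inputs give 2 × [10 × (1.960 + 0.842)/4]² = 98.1, which matches the stated 98. I assume 98 patients split 1:1, that is 49 per arm. The plan states no allocation ratio, and blocks of five cannot be 1:1 within a block. Intention to treat would cover all randomized patients, so 55 per arm (110/2) is shown as a check. Lesion rates of 1% to 10% are assumptions.

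**Step 1: the ratio.** With a events in the tenotomy arm, c in controls and n per arm, the odds ratio is a(n − c)/[c(n − a)]. With c = 0 it is infinite for a ≥ 1 and 0/0 for a = 0. This step needs no assumed rate, only that no control has surgery followed by a lesion.

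**Step 2: which of the two.** P(a ≥ 1) = 1 − (1 − p)ⁿ.

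| Assumed rate p | Infinite, n = 49 | Infinite, n = 55 |
|---|---|---|
| 1% | 39% | 42% |
| 3% | 78% | 81% |
| 5% | 92% | 94% |
| 10% | 99% | 99.7% |

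In the remaining cases the ratio is undefined.

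**Step 3: a correction does not rescue it.** For 5/49 against 0/49, adding 0.5 to each cell gives (5.5/44.5)/(0.5/49.5) = 12.2. The added 0.5 supplies the whole of the control odds. If the same kind of lesion were counted in controls and also came to 5/49, the ratio would be 1.0. Its SE(log) is √(2/5 + 2/44) = 0.667, so the 95% CI is 0.27 to 3.70.

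**Step 4: testing, as illustration only.** The plan names no test. Two-sided Fisher against 0/49 gives p = 1.0 for 1 event, 0.056 for 5 and 0.027 for 6, so six events are needed. Suppose other-toe lesions are equally common in both arms but counted in one. Then P(X ≥ 6) for X ~ Bin(49, p) is 0.3%, 3.5% and 37% at p = 3%, 5% and 10%. With 55 per arm, where six events are again needed, it is 0.6%, 5.6% and 48%. With both arms counted at 49 per arm, Fisher rejects in 0.7% of trials at 5% and 1.7% at 10%.

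**Step 5: what a one-arm report would give.** Exact 95% intervals at 49 patients: 0/49, 0 to 7.3%; 3/49 (6.1%), 1.3% to 16.9%; 5/49 (10.2%), 3.4% to 22.2%.

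**The case against.** Four points can fairly be made for the plan.

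First, a reader might infer that the ratio can never be finite, whatever the data. The documents do not support that. The analysis is by intention to treat, controls may be offered tenotomy after an ulcer, and patients who withdraw from treatment are asked to stay in follow-up. One lesion in such a control would make the ratio finite: 5/49 against 1/49 gives (5/44)/(1/48) = 5.5. The route is narrow, because the qualifying ulcer is already an endpoint and leads to the End visit. The resulting figure would still not be a fair comparison.

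Second, a reader might infer that the plan is silent on which toes are cut. Section 5.3.1 describes anaesthetizing the deformed toe or toes and then severing both flexors, which can be read as cutting every deformed toe. Section 4 presupposes that some deformed toes stay untreated. The text is ambiguous, and the number of patients with an uncut deformed toe may be small.

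Third, a reader might infer a serious risk of a falsely significant harm signal. That needs a lesion rate near 10%, for which the documents give no source. At 5% or below the risk is about 5% or less (step 4), and a single event gives p = 1.0.

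Fourth, part of the harm is already compared. Actual ulcers on uncut deformed toes of the treated foot count in the primary endpoint in both arms, and pressure points are inspected in everyone. The main gap is new impending ulcers on other toes, which have no explicit line at follow-up.

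These points limit the reach of the concern. None supplies a control-arm definition.

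**Conclusion.** The point holds for the outcome as defined. On the planned pathway the odds ratio for transfer lesion is almost certain to be infinite or undefined, and it cannot tell surgical transfer from background risk. This rests on reading the ratio as a comparison of the randomized arms, the only contrast the plan offers. The probabilities in step 2 also rest on the assumed arm size and rates; the structural zero does not.

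Tenotomy-related pain, on the same list, has the same flaw, since controls on allocated treatment have no tenotomy for pain to be associated with.

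The consequence is confined to secondary safety reporting. The change should be made because the planned figure would be uninterpretable and the remedy costs almost nothing.

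**What to change.** **Main change (section 5.8).** Remove transfer lesion and tenotomy-related pain from the odds-ratio list. Report each as a proportion of the tenotomy arm with an exact 95% confidence interval. The cost is a sentence or two of text; what is given up is a comparison with controls that the present definition cannot provide anyway.

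**Optional, if a comparison with controls is wanted.**
- Check first how many patients would have a deformed toe left uncut. If few, stop at the main change.
- At the inclusion visit, where "Randomization is performed in RedCAP", record in both arms before allocation is opened the deformed toes, those with an impending ulcer, and those that would be cut under tenotomy.
- Define the outcome in both arms as a new impending or actual ulcer after Day 0, absent at inclusion, on a deformed toe not on the would-be-cut list. Add a line for new impending ulcers by toe to the follow-up examination.
- Allow for follow-up that ends at the first ulcer, for example by analysing time to first other-toe lesion. The plan expects more ulcers in controls (10% against 6%), so they would be observed for less time and a plain count would tend to favour them.

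This costs a few REDCap fields, one form line and a reworded definition. The operator must also commit to a toe list before allocation and document departures on Day 0. The primary endpoint stays as it is under either option.
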